Statistical analysis plan (SAP)

Effects of coherent breathing breathwork on mental health and wellbeing: A randomised placebo-controlled study (NCT05676658)

[name], [name], [name]

Document date: March 15, 2023

Outcome scale measures (quantitative): Stress, anxiety, depression, well-being, sleep disturbance, credibility/expectancy of breathwork

Primary outcome of stress at post-intervention (primary timepoint) will be calculated from Depression Anxiety Stress Scale—21 items (DASS-21) stress subscale. Secondary outcomes of stress (at follow-up), anxiety and depression will be calculated from their respective DASS-21 subscales. The scores on DASS-21 subscales will be multiped by two to convert them to scores equivalent to the longer form DASS-42 score in line with scoring recommendations. Secondary outcomes of well-being and sleep disturbance will be measured by the World Health Organisation—Five Well-Being Index (WHO-5) and PROMIS Item Bank v. 1.0 - Sleep-Related Impairment—Short Form 8a, (PROMIS-8a) respectively. PROMIS-8a will be scored using a T-score transformation according to PROMIS Sleep scoring manual. Pre-intervention, post-intervention (after 28 days) and follow-up (after a further 28 days) scale score differences between groups will be analysed through mixed analysis of variance.

Self-reported credibility and expectancy of the breathwork protocol will be measured via the Credibility/Expectancy Questionnaire (CEQ-6). Descriptive statistics for all measures for all participants in each condition will be reported. Missing items within scales will be replaced using the mean for other items in the scale/subscale in cases where = <30% of items are missing for a scale/subscale. Multiple imputation will be used where >30% of data is missing from a scale/subscale or where whole scales/subscales are missing. Cronbach's alphas will be used to assess internal consistency of each scale at baseline.

Primary analysis

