Intention-to-treat; using an independent t-test to see if there is a difference. Post-intervention is the primary timepoint for primary outcome stress. For both the primary outcome and secondary scale outcomes, group x time effects at the p<.05 level will be determined using mixed ANOVAs. Group x time effects at the p<.05 level will be followed up with simple contrasts (with pre-intervention as the comparator) and Bonferroni-corrected within-group t-tests. Baseline data will be controlled for depending on the outcome being tested (i.e., DASS Stress at baseline will be entered as a covariate when testing effects on DASS Stress). Data analysis will be performed in R and SPSS.

Secondary analysis

Per-protocol analysis (participants completing at least 14 sessions [50%] of the breathwork) will be conducted as secondary analysis.

Sensitivity checks

If sizeable missing data are present (greater than 5%), they will be replaced using multiple imputation, and used for sensitivity analysis. Analysis without baseline covariates will be included as sensitivity analysis. The DASS, WHO, and PROMIS all have one attention-check question in them to ensure participants are completing the surveys properly. If a participant answers more than one incorrectly at each timepoint their data will be excluded from the main analyses but included in a sensitivity analysis. The same applies to those who state that their breathwork practice was significantly impaired in response to the question on impairment of practice below.

Exploratory analysis of secondary measures (quantitative)

Adherence to breathwork protocol

Post-intervention, participants will answer how many times they completed the guided breathwork out of the assigned 28 days. This will be compared between groups via unpaired t-test, and correlated with outcome scale scores on DASS, WHO and PROMIS within each condition to see whether there are any associations between adherence and changes in these scale scores. Adherence will be looked at as a moderator.

Credibility/expectancy of breathwork protocol

Similar to adherence, CEQ scores will be correlated with the outcome scale scores above, to see whether there are relationships between CEQ and changes in these scale scores within each condition. CEQ scales will be compared between groups via unpaired t-tests. If there are significant differences between groups on credibility/expectancy, it will be used in covariance analysis.

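### The SAP is inconsistent on whether imputed data feed the primary intention-to-treat test of stress, excludes participants after randomisation from the main analyses, and plans no check on departure from missing at random

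*SAP*

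**What the plan says.** **Missing outcomes.** The opening section of the SAP, on outcome scales, states: "Multiple imputation will be used where >30% of data is missing from a scale/subscale or where whole scales/subscales are missing". It names no analysis to which this applies. Under Sensitivity checks the SAP states: "If sizeable missing data are present (greater than 5%), they will be replaced using multiple imputation, and used for sensitivity analysis". Neither sentence refers to the other.

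**Primary test.** Under Primary analysis: "Intention-to-treat; using an independent t-test to see if there is a difference". The input dataset is not named. The same paragraph brings in mixed ANOVAs and says "DASS Stress at baseline will be entered as a covariate when testing effects on DASS Stress". Sensitivity checks adds "Analysis without baseline covariates will be included as sensitivity analysis", which suggests that the adjusted model is the main one.

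**Exclusions.** For participants who fail more than one attention check, Sensitivity checks says "their data will be excluded from the main analyses but included in a sensitivity analysis". It continues: "The same applies to those who state that their breathwork practice was significantly impaired in response to the question on impairment of practice below". The SAP section on Impairment of Practice describes that item as optional, answered yes or no with free text, and asked at post-intervention.

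**Expected loss.** The protocol (Methods, Participants) recruits 400 so as to retain the 260 needed, and mentions that the platform has seen attrition of up to 50%.

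**The concern.** A participant who never returns the post-intervention survey is missing the whole stress subscale. One SAP sentence says this person is imputed. Another says imputed data serve sensitivity analysis. A reader cannot tell which result is the primary one, and the choice could be made after both have been seen.

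The exclusions are a separate departure from the label. Impaired practice is reported after randomisation and may depend on the assigned breathing pace, because pace is the one feature in which the two audios differ. Removing such people can therefore select differently in the two arms. The item carries no threshold for what counts as significant impairment, so the decision rests on reading free text. Only people who return the survey and choose to answer can be excluded this way.

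Finally, multiple imputation from baseline assumes missing at random. If people stop responding because their stress has not improved, and do so more in one arm, imputation and a completer analysis go wrong together and nothing planned would show it. The protocol's Background states low risk of bias as the aim of the trial, so this bears on its purpose.

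**Working it through.** **1. The plan's own figures.** Inputs from the protocol (Participants): d = 0.35, alpha 0.05, power 0.80; two-sided testing is assumed. The normal formula gives 129 per arm (258 in total). The t-based solution is 129.1, rounded up to 130 per arm, or 260 in total, so the stated figure reproduces. Implied loss: 1 − 260/400 = 35%, or 140 people. The quoted maximum of 50% would be 200 people.

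**2. Is imputation triggered?** The 5% has no stated denominator. As participants it is 0.05 × 400 = 20; as survey returns over three timepoints it is 0.05 × 1,200 = 60. A loss of 140 post-intervention scores is 35% of the first or 140/1,200 = 11.7% of the second. The trigger is met either way.

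**3. Does the dataset choice move the estimate?** Illustrative simulation, 1,000,000 per arm, with these assumptions: no true effect; SD 1; baseline–post correlation r = 0.5; dropout fixed at 35% or 50% in each arm; logistic dropout with the slopes shown (log-odds per SD of higher stress, coherent v sham). Negative values favour coherent breathing. Entries are bias in SD at 35% / 50% loss.

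Dropout depends on baseline stress:

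| Slopes | Unadjusted t-test | Completer ANCOVA and imputation by arm |
|---|---|---|
| 0.5 v 0 | −0.085 / −0.117 | within 0.003 of zero |
| 0.7 v 0 | −0.112 / −0.161 | within 0.003 of zero |
| 0.7 v 0.5 | −0.029 / −0.037 | within 0.003 of zero |
| 0.7 v 0.7 | 0.000 / −0.004 | within 0.003 of zero |

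Dropout depends on post-intervention stress:

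| Slopes | Completer ANCOVA | Imputation by arm |
|---|---|---|
| 0.5 v 0 | −0.127 / −0.177 | −0.127 / −0.178 |
| 0.7 v 0 | −0.170 / −0.235 | −0.173 / −0.237 |
| 0.7 v 0.5 | −0.045 / −0.062 | −0.047 / −0.063 |
| 0.7 v 0.7 | 0.002 / −0.001 | 0.003 / −0.002 |

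With the covariate, completer and imputed results differ by at most 0.003 SD in the second table. Range over r for ANCOVA with dropout on the post score: one arm only, −0.151 to −0.285 at r = 0.3 and −0.085 to −0.164 at r = 0.7; slopes 0.7 v 0.5, −0.052 / −0.071 and −0.030 / −0.043.

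**4. What a delta analysis would report.** Suppose the adjusted estimate is a benefit of 0.35 SD and coherent-arm dropouts are worse than missing at random predicts by delta SD. The benefit falls by loss × delta. The standard error at r = 0.5 is sqrt(4 × 0.75/n).

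- 35% loss, n = 260: SE = 0.107. Significance is lost at delta = (0.35 − 1.96 × 0.1074)/0.35 = 0.40 SD. The benefit is cancelled at 0.35/0.35 = 1.0 SD.
- 50% loss, n = 200: SE = 0.122. Significance is lost at (0.35 − 1.96 × 0.1225)/0.50 = 0.22 SD. The benefit is cancelled at 0.35/0.50 = 0.7 SD.

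**5. The exclusions.** The documents give no expected frequency for failed attention checks or impaired practice, so their effect is not sized here. The contradiction with the label is textual.

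**The case against.** A reader might infer that the primary analysis is completers-only: the Sensitivity checks sentence is the only one that gives imputed data a use, and the sample size counts on 260 of 400 remaining. The documents do not establish this. The opening section's imputation rule is unrestricted, and the intention-to-treat label also points towards imputed data. What stands is a conflict between the two sections.

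A reader might also make much of the missing denominator for the 5%. Step 2 shows that it changes nothing at the loss the protocol allows for.

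The 35% and 50% should not be read as forecasts. They are an allowance and a past maximum, and the protocol sets prescreeners, payment per survey and reminder messages to limit loss.

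The best defence concerns size. Under the planned covariate the choice of dataset hardly matters, and the larger biases need score-related dropout in one arm only. That is extreme, because the protocol (Intervention and Comparator) matches the arms on everything but pace. This defence stands, and it limits the point on the dataset. It does not answer outcome-dependent dropout, which the covariate does not remove, or the exclusions.

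The excluded participants do return in a sensitivity analysis. That is a partial safeguard, but it makes the selected set the main result.

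One could add that a three-timepoint ANOVA ("follow-up (after a further 28 days) scale score differences between groups will be analysed through mixed analysis of variance") would discard people lacking follow-up. That follows only if this ANOVA is the primary test and follow-up is not imputed, and the SAP settles neither.

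**Conclusion.** The concern holds and should be fixed, in three parts.

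- **Dataset.** The SAP's two imputation rules conflict on what feeds the primary test. The numerical consequence is small under the planned covariate. It matters mainly if the unadjusted t-test is primary: −0.08 to −0.16 SD with baseline-related dropout in one arm only, about −0.03 to −0.04 SD with slopes 0.7 v 0.5, about zero with equal slopes.
- **Analysis set.** As written, the main analysis is not intention-to-treat, because it drops people on information gathered after randomisation, partly by an undefined criterion.
- **Missing not at random.** No planned analysis addresses it. Dropout on the post score would bias completer and imputed results alike: −0.13 to −0.24 SD in the one-arm extreme, about −0.045 to −0.06 SD with slopes 0.7 v 0.5, about zero with equal slopes.

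The bias figures are illustrations resting on r = 0.5, the chosen slopes and 35–50% loss. They do not predict bias in this trial. The textual findings need no assumption.

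**What to change.** Revise the SAP's Primary analysis and Sensitivity checks sections as follows.

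1. Name one baseline-adjusted primary analysis of post-intervention stress that uses every observed post-intervention score. Two options are a likelihood mixed model with post-intervention and follow-up as outcomes and baseline stress as covariate, or multiple imputation by arm feeding the baseline-adjusted comparison. Say whether the observed-data or the imputed result is primary, and align the imputation sentence in the opening section. The 5% trigger can then be dropped or given a denominator.
2. Make the analysis of all randomised participants primary, and move the attention-check and impaired-practice exclusions to a sensitivity analysis, with a written rule for what counts as significant impairment.
3. Add one delta-shift sensitivity analysis for coherent-arm dropouts, for example 0 to 1.0 SD in steps of 0.2, and report the shift at which p<.05 is lost.

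The cost is SAP wording and a little more R code, with no new data. The downside is slightly more analysis work and possibly a less favourable sensitivity result.

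### The primary analysis is called intention-to-treat, yet participants who report after randomisation that their practice was significantly impaired are left out of the main analyses

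*SAP*

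**What the plan says.** The SAP's Primary analysis section opens with "Intention-to-treat; using an independent t-test to see if there is a difference" and names post-intervention as the primary timepoint for stress.

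Under Sensitivity checks, the SAP says of participants who fail attention checks that "their data will be excluded from the main analyses but included in a sensitivity analysis". The condition that triggers this is worded as follows: "If a participant answers more than one incorrectly at each timepoint". The next sentence extends the exclusion to impaired practice: "The same applies to those who state that their breathwork practice was significantly impaired in response to the question on impairment of practice below".

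The question itself is described in the SAP under Impairment of Practice and in the Protocol under Secondary Outcome Measures. It is optional, is put at post-intervention, concerns the randomly allocated breathwork, and takes a yes/no answer with free text. Randomisation comes earlier, straight after the pre-intervention survey (Protocol, Randomisation and blinding).

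Low adherence is treated differently: "Per-protocol analysis (participants completing at least 14 sessions [50%] of the breathwork) will be conducted as secondary analysis".

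**The concern.** Intention-to-treat means that everyone randomised is analysed in the allocated arm, whatever happens afterwards. Here the headline comparison drops people because of an answer given after about four weeks of the allocated practice. Pace is the only intended difference between the arms (5.5 against 12 breaths per minute), and pace could affect whether practice felt impaired. Selecting on such an answer can undo the balance that randomisation created.

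Three features make the rule harder to defend.

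- It has no threshold. The answer is yes/no plus free text, so someone must judge what counts as significant. The Protocol's Procedure section sets up separate post-intervention surveys per condition, so answers arrive sorted by arm, and no blinded coding is described.
- The question is optional, so a participant who was impaired but skips it stays in.
- The hierarchy is inverted. Doing fewer than 14 sessions removes someone only from a secondary analysis, while reporting impairment removes them from the main one.

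Attention-check failures after randomisation raise the same issue to a smaller degree. At stake is who is counted in the primary result of a trial whose stated aim is low risk of bias.

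**Working it through.** **1. The text.** The words 'the same applies' can refer only to the preceding sentence, which excludes people from the main analyses and returns them in a sensitivity analysis. No section exempts the primary stress comparison or defines a modified intention-to-treat set. The label and the rule therefore define two different primary sets. This step needs no assumption.

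**2. The plan's own sample size.** For d = 0.35, two-sided 5% and 80% power, the t-test calculation gives 129.1 per arm, rounded up to 130, or 260 in total. The Protocol's figure reproduces, and 130 per arm is used below.

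**3. Size of a possible bias.** From the documents come 130 per arm and baseline adjustment ("DASS Stress at baseline will be entered as a covariate when testing effects on DASS Stress"). Everything else is assumed: no true effect, a baseline-to-post correlation of 0.6, excluded people 0.5 SD more stressed than retained people in both arms, and exclusion of 15% (coherent) against 5% (placebo).

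- Bias in the post-intervention difference = (p1 − p0) × gap = (0.15 − 0.05) × 0.5 = 0.050 SD.
- If the gap arises wholly after baseline, adjustment removes none of it, and the bias stays 0.050 SD.
- If the excluded were equally worse at baseline, adjustment leaves 0.050 × (1 − 0.6) = 0.020 SD.
- Numbers left: 130 × 0.85 = 110.5 and 130 × 0.95 = 123.5. Unadjusted SE = √(1/110.5 + 1/123.5) = 0.131. Adjusted SE = 0.131 × √(1 − 0.6²) = 0.105.
- Type I error = P(|Z + bias/SE| > 1.96):

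| Excluded, coherent v placebo | Gap equal at baseline | Gap wholly after baseline |
|---|---|---|
| 10% v 10% | 5.0% | 5.0% |
| 10% v 5% | 5.1% (bias 0.010) | 5.7% (bias 0.025) |
| 15% v 5% | 5.4% (bias 0.020) | 7.6% (bias 0.050) |

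A simulation of 20,000 trials at 15% v 5% gave 5.4% and 7.4%, in line with the last row.

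**4. Direction.** If the excluded are more stressed, dropping more of them from the coherent arm favours coherent breathing. Swapping the rates, or making the excluded less stressed, reverses the sign. Equal rates can still mislead if the gap differs by arm: 10% excluded in each, with a 0.5 SD gap in one arm only, gives 0.10 × 0.5 = 0.05 SD unadjusted. With no gap there is no bias.

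**5. Dependence on the test.** The SAP names an independent t-test, mixed ANOVA and a baseline covariate without making clear which is primary. For 15% v 5%, an unadjusted comparison gives 0.050/0.131 = 0.38 SE, an error of 6.7%. A change-score comparison has SE = 0.131 × √(2 × (1 − 0.6)) = 0.117. It gives 5.0% when the gap is equal at baseline, because the bias cancels, and 7.1% when it is not.

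**6. Power.** With 10% excluded, 260 remain for analysis as long as attrition is at most 1 − 260/(0.90 × 400) = 27.8%. Only if attrition has already brought the trial down to 260 does a 10% exclusion leave 234 and lower unadjusted power from about 80% to 76%.

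**The case against.** The strongest reply is that nothing is hidden. The exclusion is prespecified, and so is the analysis that restores the excluded people, so both estimates will exist and a reader can compare them. Self-assessed screening, an optional question and the word 'significantly' may keep exclusions few. The larger error figure needs a three-fold imbalance, a 0.5 SD gap, and that gap arising wholly after baseline. No document supports any of these.

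All of that stands as a limit on size. It does not settle which analysis is primary: the restricted set supplies the headline under a label that does not describe it.

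A reader might infer more than the documents support:

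- **That the rule inflates the benefit of coherent breathing.** Nothing shows which arm would lose more people, or whether those people would be more stressed.
- **That the trial will be underpowered because of the rule.** That follows only if attrition has first used up the margin between 400 recruited and 260 needed.
- **That every attention-check exclusion biases the comparison.** Baseline checks precede randomisation and do not.

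**Conclusion.** The contradiction is certain: as written, the headline stress comparison is not intention-to-treat, because it selects on an answer given after randomisation that treatment could influence. The size and sign of any bias are unknown. In the illustration, bias is zero with equal rates and equal gaps, and 0.02 to 0.05 SD (type I error about 5.4% to 7.6%) at 15% v 5% excluded. Those figures rest on the assumed rates, gap and correlation, and on reading the primary test as baseline-adjusted. The case for changing the SAP rests on the conflict between label and rule in the primary analysis, and not on these numbers.

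**What to change.** Define the primary analysis set as all randomised participants in their allocated arm, regardless of reported impairment or of attention-check results after randomisation. Make both exclusions sensitivity analyses, and report the numbers excluded by arm. State separately whether participants who failed attention checks at baseline stay in the primary set.

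For the sensitivity analyses:

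- Define 'significantly impaired'. A plain yes would be broader than the present rule.
- Say whether 'at each timepoint' means any timepoint or every one.
- Have the free text coded without sight of allocation, for example with survey identifiers removed first.

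The cost is SAP wording and slightly noisier data from impaired or inattentive participants. Recruitment, eligibility and data collection do not change. The SAP's differing statements on where multiple imputation is used are a separate issue, to be settled on their own.

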# Secondary Hypotheses

 Coherent breathing breathwork practice for ~10min/day over a 4-week period will lead to greater reduction in self-reported stress than practice of a placebo control breathwork practice at follow-up.

- Coherent breathing breathwork practice for ~10min/day over a 4-week period will lead to greater reduction in self-reported anxiety than practice of a placebo control breathwork practice at: a) post-intervention, b) follow-up.
- Coherent breathing breathwork practice for ~10min/day over a 4-week period will lead to greater reduction in self-reported anxiety than practice of a placebo control breathwork practice at: a) post-intervention, b) follow-up.
- Coherent breathing breathwork practice for ~10min/day over a 4-week period will lead to greater reduction in self-reported depression than practice of a placebo control breathwork practice at: a) post-intervention, b) follow-up.
- Coherent breathing breathwork practice for ~10min/day over a 4-week period will lead to greater increase in self-reported well-being than practice of a placebo control breathwork practice at: a) post-intervention, b) follow-up.
- Coherent breathing breathwork practice for ~10min/day over a 4-week period will lead to greater reduction in sleep disturbance than practice of a placebo control breathwork practice at: a) post-intervention, b) follow-up.
- There will be no significant differences between intervention and placebo groups on the: a) credibility and b) expectancy of the breathwork randomly assigned to groups.

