# Outcome measures

All outcomes (primary, secondary, other) are mentioned below. Pre-post intervention and follow-up questionnaires will be self-completed by participants online via the survey platform Qualtrics, which will be linked to Prolific. Three short scales will be used to measure outcomes of mental health, well-being and sleep disturbance at these timepoints (baseline/pre-intervention, post-intervention, 1-month follow-up): the Depression Anxiety Stress Scale (DASS-21) (Lovibond, & Lovibond, 1995), World Health Organisation- Five Well-Being Index (WHO-5) (WHO, 1998) and PROMIS Item Bank v. 1.0 - Sleep-Related Impairment - Short Form 8a (Hanish, Lin-Dyken & Han, 2017). The primary outcome will be stress (measured using the DASS-21 stress subscale), and the primary timepoint will be postintervention (four weeks post-randomisation). The secondary outcomes will be: anxiety and depression (from DASS-21) well-being (WHO-5) and sleep disturbance (PROMIS). Immediately after starting the breathwork, participants will be asked about the credibility/expectancy of the intervention randomly allocated to them to assess if the intervention and placebo are seen as equally credible and thus merit equal expectation of benefit. This will be measured using the 6-item Credibility/Expectancy Questionnaire (CEQ) (Devilly & Borkovec, 2000), which is another secondary outcome. The last secondary outcome, which will be measured post-intervention, is: adherence (number of times participants self-reported practicing breathwork out of the 28days assigned). Other outcomes include an open-ended question on participants overall experiences of the protocol and/or study period. Pre-intervention, simple demographics (Age, Gender and Ethnicity) will be collected and, post-intervention/follow-up, participants will be asked if anything impaired their ability to perform the breathwork, and if they can guess the study hypothesis (to tentatively see if blinding was successful—see Procedure section).

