# Secondary Outcome Measures:

- 2. Subjective anxiety (DASS-21 anxiety subscale)
- 3. Subjective depressive symptoms (DASS-21 depression subscale)
- 4. Subjective wellbeing (WHO-5)
- 5. Subjective sleep disturbance (PROMIS-8a)

All of above outcomes measured pre-post-follow-up.

- 6. Self-reported credibility and expectancy of protocol (CEQ-6) . Measured after completing first session of breathwork.
- 7. Self-reported adherence to breathwork protocol (number of sessions participants self-report practicing out of 28 days assigned). Measured post-intervention.

Other—Overall experience, Impairment of practice, Hypothesis guessing, Attention checks
Optional open-ended questions on participants' perspectives and overall experience of the
protocol (post-intervention) / study-period (follow-up), whether anything impaired
participants' ability to perform their randomly allocated breathwork (post-intervention), and
if they can guess the hypothesis of the study (follow-up). Lastly, The DASS, WHO, and

PROMIS will all have one attention-check question in them to ensure participants are completing the surveys properly.

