# Intervention and Comparator

Both groups will also be provided with an identical ~5min introductory/welcome audio to the study which they can listen to on the first day.

Participants in intervention group will be randomised to a guided audio of coherent breathing (at ~5.5.bcpm with equal inhales/exhales of ~5.5secs each without deliberate pauses), for 28days (4weeks), pre-recorded by a trained breathwork facilitator, delivered remotely online. The average coherent breathing rate for maximising HRV is around 5.5bcpm so this cadence was chosen for the intervention group. The duration of ~10min was deemed as a manageable time for participants, and several studies (ranging from days to weeks) on meditation have shown benefit can be derived from this short length of practice.

Participants in control group will be randomised to a guided audio of placebo 'sham' coherent breathing breathwork (12bcpm with equal inhales/exhales of 2.5secs each without deliberate pauses) for ~10mins/day, for 28days (4weeks), pre-recorded by a trained breathwork facilitator, delivered remotely online. The metric of 12bcpm is in line with guidance from the British Journal of Nursing, Royal College of Physicians, and Johns Hopkins University which state that the average, healthy bcpm should range from: 12-18bcpm, 12-20bcpm, and 12-16bcpm, respectively, hence we chose the minimum for the control group.

12 bcpm is highly unlikely to be difficult or detrimental to anyone based on BJN, RCP, and JHU guidance as it is at the lower bound of bcpm for typical resting breathing for adults.

The intervention/control audios are identical (exact same sound and instruction). The placebo control is matched to the active intervention in all domains but pace of breathing.

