### Randomisation and blinding

The type of study is participant blinded RCT with assessor blinded data collection (that is assessor is not present for data collection which is self-completed by the participant on a survey software platform). After completing the pre-intervention survey, participants will be randomly assigned, via the online survey software Qualtrics using block randomisation (1:1), to receive either the intervention coherent breathing breathwork (5.5bcpm), or placebo coherent breathing breathwork (12bcpm). Participants will be blinded to their intervention (concealment)—the technique of breathwork will be referred to as 'rhythmic breathing' in both the active intervention and placebo control breathwork audios, in an attempt to blind participants to the intervention being used.

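### The hypothesis of no significant credibility or expectancy difference is met simply by failing to reject: the only between-arm test is a t-test, with no confidence interval or margin

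*SAP*

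**What the plan says.** The protocol's Secondary Hypotheses include: "There will be no significant differences between intervention and placebo groups on the: a) credibility and b) expectancy". Its Outcome measures section says the Credibility/Expectancy Questionnaire (CEQ) is given "to assess if the intervention and placebo are seen as equally credible and thus merit equal expectation of benefit".

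The SAP section on credibility/expectancy, which sits under the exploratory heading, supplies the test: "CEQ scales will be compared between groups via unpaired t-tests". It adds: "If there are significant differences between groups on credibility/expectancy, it will be used in covariance analysis". It also plans correlations of CEQ with outcomes within each arm, which are not between-arm comparisons.

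The protocol's list of secondary outcomes gives one CEQ assessment: "Measured after completing first session of breathwork". The mixed ANOVA planned for the repeated scales therefore cannot apply to it. The SAP promises descriptive statistics by arm for all measures. Neither document gives a confidence interval for the CEQ difference, a margin, an equivalence test or a power statement for CEQ.

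**The concern.** The stated purpose is to judge whether the arms are equally credible, but the stated criterion is absence of significance. A t-test that fails to reject can reflect a small gap or an imprecise estimate, and the p-value alone does not say which. The incentive also runs the wrong way, because poor CEQ response makes the hypothesis easier to meet.

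This matters because the trial's claim rests on its control. The protocol says "The placebo control is matched to the active intervention in all domains but pace of breathing", the main outcomes are self-reported, and the exploratory hypotheses themselves expect higher credibility/expectancy to go with greater improvement. CEQ is the planned check on equal expectation. The other blinding check, hypothesis guessing, is optional and described as tentative.

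There is a lesser point about the covariate rule. The protocol says "After completing the pre-intervention survey, participants will be randomly assigned", and CEQ follows the first session, so CEQ is a post-randomisation variable. An estimate adjusted for it is not the total treatment effect, and no reason is given for fitting that model only when the arms differ significantly.

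**Working it through.** **Inputs.** From the protocol's Participants section: 400 recruited, 200 per arm; 260 needed, which is 260/2 = 130 per arm; attrition of up to 50%, which gives 0.5 × 200 = 100 per arm. Allocation is 1:1. Sidedness is not stated, so two-sided 0.05 is assumed. The documents give no CEQ standard deviation, so all gaps are in CEQ SD units. They are not comparable with the stress effect size of d = 0.35.

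**The plan's own figure.** For stress, n per arm = 2(1.96 + 0.84)²/0.35², which rounds up to 129 (258 in total). The exact t solution is 129.1, so 130 per arm and 260 in total. The stated 260 reproduces with a two-sided test. No corresponding figure exists for CEQ.

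**1. Chance that one scale is non-significant despite a true gap d.** The test statistic is noncentral t with 2n − 2 degrees of freedom and noncentrality d/√(2/n). At n = 200, √(2/n) = 0.100, so d = 0.20 gives noncentrality 2.0 against a critical value of 1.966.

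| True gap | 200 per arm | 130 | 100 |
|---|---|---|---|
| 0.20 SD | 0.486 | 0.638 | 0.709 |
| 0.35 SD | 0.063 | 0.197 | 0.308 |

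**2. Both scales non-significant, same gap on both.** Simulated with an assumed between-scale correlation of 0.3 to 0.7. For a 0.20 SD gap at 200 per arm: about 28–36%. For a 0.35 SD gap: about 1–3% at 200 per arm, 6–11% at 130 and 13–20% at 100.

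**3. What a non-significant result leaves open.** The 95% half-width is t(0.975) × √(2/n): 0.197, 0.244 and 0.279 SD at 200, 130 and 100 per arm. Share of non-significant results whose 95% interval still reaches a given gap on either side, when the true gap is zero (simulated):

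| Interval reaches | 200 per arm | 130 | 100 |
|---|---|---|---|
| 0.20 SD | 96% | 100% | 100% |
| 0.35 SD | 8% | 36% | 60% |

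The first row follows almost directly from the half-widths: at 0.197 SD, only an estimate very close to zero gives an interval that stays inside 0.20 SD.

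**4. The covariate trigger.** With no true gap on either scale, at least one test is significant in about 8–10% of trials (same correlation range; 1 − 0.95² = 9.75% under independence).

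**The case against.** The strongest reply is that little depends on this check. The primary stress analysis does not use CEQ, a non-significant CEQ result triggers nothing, and the documents nowhere say that non-significance will be reported as equality. Descriptives by arm are promised, so a reader could work out an interval. CEQ is collected after the first session, before most dropout, so 200 per arm is the more relevant case. There a 0.35 SD gap is missed 6% of the time on one scale and 1–3% on both. Nothing in the documents makes 0.20 SD important. The covariate rule is labelled exploratory and is not said to replace the main analysis.

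Most of this is fair and limits the weight of the point. It does not repair the criterion. Credibility and expectancy are separate parts of the hypothesis, so single-scale figures are relevant. Because the documents do not say what gap would matter, a reader needs the interval, and the plan neither commits to one nor bases its conclusion on one. CEQ is also a separate survey, so non-response cannot be excluded. On the covariate rule, the objection leaves only a modest exploratory issue.

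**Conclusion.** The concern holds. As written, failing to reject meets the hypothesis, and that does not show equal credibility or expectancy. At full response, non-significance usually excludes a 0.35 SD gap but almost never a 0.20 SD gap; at 100 per arm it often excludes neither. This should be corrected, but it does not threaten the primary result.

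The figures assume two-sided 0.05 tests, equal arms and, for joint results, a between-scale correlation of 0.3 to 0.7. The 130 and 100 scenarios borrow the stress requirement and a general attrition figure, so they are assumptions about CEQ response. If the SAP's multiple imputation covers missing CEQ, it would not fully restore precision. The covariate trigger is a secondary point on which the conclusion does not depend.

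**What to change.** **Main change.** In the protocol's Secondary Hypotheses and the SAP's credibility/expectancy section, replace the non-significance criterion with wording such as: *The difference between arms in credibility and in expectancy will each be reported with a 95% confidence interval and the number of respondents per arm. A non-significant difference will not be taken as evidence of equal credibility.*

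**If equivalence is to be claimed.** Restate the hypothesis as equivalence, set a margin justified for the CEQ in advance, and require the 90% interval for both scales to lie inside it.

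**Covariate rule.** Remove the significance trigger. State that the estimate without CEQ is the treatment effect, and report any CEQ-adjusted model as exploratory whatever the p-value.

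**Cost.** Wording only, on the same data; reporting intervals without an equality claim costs nothing more. An equivalence claim is harder to reach. With zero true gap, the simulated chance that both scales succeed (correlation 0.3 to 0.7) is:

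| Illustrative margin | 200 per arm | 130 | 100 |
|---|---|---|---|
| 0.25 SD | 38–44% | 9–11% | 1–2% |
| 0.30 SD | 69–73% | 32–38% | 14–17% |
| 0.35 SD | 88–89% | 59–64% | 36–42% |

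No margin is recommended here, because the documents give no basis for one.
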